3.1 General Design

This is a two-phase study. Phase 1 will evaluate obesity-related behavioral and biological characteristics as potential mechanisms of non-response to BT. Phase 2 is a double-blind, placebo-controlled, RCT to test whether augmenting BT with weight loss medication improves 24-week weight loss, as compared to BT with placebo, in subjects identified as early non-responders to 4 weeks of individual behavioral weight control. Subjects will be a total of 150 adults, aged 21-70 years, with a body mass index (BMI) of 31 kg/m² or above (28 kg/m² with an obesity-related comorbidity). Subjects will attend a screening visit in which they will complete a behavioral evaluation with a psychologist and a medical history. In phase 1, eligible subjects will complete questionnaires and an in-person baseline assessment of obesity-related behavioral characteristics (satiety, hunger, RRV_{food}, and impulsivity), neuropeptides, and gastric emptying. Within 2 weeks of this assessment, they will begin an initial 4-week BT “run-in” delivered individually in 20-30 minute sessions. The primary goal of phase 1 will be to evaluate baseline postprandial satiety, postprandial change in GLP-1, and gastric emptying as predictors of early weight loss after 4 weeks of BT. We will also examine whether these variables predict categorization as an early non-responder to BT who loses < 2.0% of initial weight (vs. early responders who lose ≥ 2.0%; approximately 33% vs. 66% of the sample, respectively).

In phase 2, early non-responders (who lost < 2.0% during the BT run-in) will be randomly assigned to 24 weeks of: 1) BT plus placebo (BT+P); or 2) BT plus medication (BT+M; phentermine 15.0 mg). Both treatment groups will continue to attend 20-30 minute individual BT sessions, weekly for the first 12 weeks and every other week for the last 12 weeks (total of 18 visits). Both treatment groups will also take once daily study medication (placebo or phentermine 15.0 mg) for the duration of the intervention period (with titration between randomization and week 2). Early BT responders identified during the run-in will receive the same 24-week BT program, but will not receive study medication or be included in the randomized trial. The assessments administered at baseline – questionnaires, including behavioral testing, blood draws, and measurements of body weight – will be repeated at randomization (week 0) and at week 24.

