9.1 Sample Size and Power Determination

A total sample size of 150 subjects will provide at least 80% power to detect all three primary outcomes. All power analyses were conducted using G*Power 3.1 at an alpha of .05. A correction for multiple comparisons is not proposed due to the preliminary nature of this research.

Phase 1: For the co-primary outcome - percent weight loss at the end of the BT run-in as predicted by baseline satiety, postprandial GLP-1, and gastric emptying - an estimated effect size for each predictor of

$\rho^2 = .042$ was selected as the lower estimate from studies predicting weight loss from VAS satiety ratings and GLP-1 (ρ 's $\geq .20$).^{16, 106} (We did not find studies using gastric emptying to predict weight loss, and the effect sizes for comparisons between BMI categories of $\rho^2 = .07 - .30$ were less conservative.^{43, 78}) Based on this estimate, a sample size of 150 subjects would yield 80% power to detect statistical significance for the three individual predictor variables. The second co-primary outcome - non-responder status as predicted by these three predictors in discriminant analysis - would have 90.1% power with this sample size, based on power analysis for a 2-group MANOVA for 3 response variables^{107, 108} with an estimated combined effect size of $\rho^2 = .10$.

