Phase 2: For the primary outcome - percent weight change from randomization to week 24 among early non-responders - estimated group means, variances, and attrition rates were derived from data from prior studies conducted at our Center and from previous research in early non-response to BT e.g.,⁴. The estimated treatment effect is based on the placebo-subtracted effect of 28 weeks of phentermine 15.0 mg of 4.5 kg (4.4% of initial weight), as determined by a multi-arm RCT that enrolled 219 total patients in the placebo and phentermine 15.0 mg groups.⁷⁷ We selected this result as the basis of our power analysis because it most closely matched the phentermine dose and duration used in the present study. Other previous RCTs examining the effect of phentermine monotherapy have typically administered a 30.0 mg dose for 12 to 16 weeks. The majority of these trials have achieved larger placebo-subtracted weight losses of 5.4 to 7.8 kg.^{72, 74-76} (One randomized trial reported a 4.0 kg placebo-subtracted loss with a different formulation, phentermine resin 30.0 mg,⁷³ and one reported a 3.3% placebo-subtracted loss when both phentermine 37.5 mg and placebo were combined with a 900-1100 kcal/day meal replacement diet, resulting in large mean weight losses in both groups.¹⁰⁹) An additional study suggested that the difference in mean weight loss between phentermine 15.0 mg and phentermine 30.0 mg (both when combined with lorcaserin) is small (0.6 kg mean difference).¹¹⁰ We therefore believe that participants provided with 24 weeks of phentermine 15.0 mg are likely to achieve a placebo subtracted loss of $\geq 4.5\%$ of initial weight. (Most early phentermine studies reported results in kg, which is roughly equivalent to percent weight loss in populations with obesity.)

We predict a 24-week post-randomization weight loss among early non-responders of 6.5% in BT+M and 2.0% in BT+P, with expected standard deviations of 5.5%. We expect 33% of the initial baseline sample of 150 subjects to be categorized as early non-responders following the BT run-in.^{4, 7, 8} Based on these estimates, a randomized sample size of 50 non-responders (25 per group), assuming a 20% attrition rate, will give us 81.5% power to detect between-treatment group differences at week 24 of 4.5% (effect size: $d = 0.82$).

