9.2 Statistical Methods

Data quality and integrity will be checked by assessing the data for missing and out-of-range values and univariate normality with basic statistical procedures, including descriptive statistics and visual graphical displays (e.g., histograms, scatter plots). All questions of data quality and integrity will be investigated before any statistical modeling is conducted. To test the adequacy of randomization, preliminary analyses will include a comparison of demographic and baseline characteristics between randomized treatment groups (BT+P and BT+M; t-tests or Wilcoxon rank sum tests for continuous variables and Chi-Square test or Fisher's Exact test for categorical data). If baseline imbalances are observed, the relevant variables will be included as covariates in analyses relevant to those outcomes.

All analyses will be conducted using the ITT principle. Analyses will be two-tailed with an alpha of 0.05, and will be conducted using SPSS version 24.0 or SAS version 9.4. For all analyses, residual analyses will be conducted to check for outliers, influential points, and violations in the normality assumption. If violations are detected, variance-stabilizing transformations will be considered.

Phase 1: Analyses will be based on the initial population of subjects who attend at least one post-baseline treatment visit during the BT run-in. Multiple regression will be used to evaluate predictors of early weight loss with BT (% loss at week 0) and discriminant analysis will be used to assess which variables predict categorization as a non-responder (who has lost $< 2\%$ of initial weight at week 0). The primary analyses will test the hypothesis that the set of baseline satiety measures (VAS satiety ratings, postprandial changes in GLP-1, and gastric emptying) predict these outcomes when considered simultaneously. Additional analyses will evaluate demographic characteristics, secondary predictor variables (fasting hunger, RRV_{food}, reinforcing efficacy of food, impulsivity, fasting ghrelin, fasting leptin, and lower postprandial changes in insulin and PYY), and exploratory variables as predictors of early weight loss.

Factor analysis will be used to assess whether predictor variables cluster into phenotypes.

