Phase 2: Primary analyses will be based on the all-randomized population. The null hypothesis being tested is that there will be no significant difference between non-responders assigned to BT+M and BT+P in mean percentage of initial weight lost at 24 weeks post-randomization. To assess the primary phase 2 outcome of percent weight change by treatment group (among non-responders), a mixed effects model will be fit with treatment group (BT+P, BT+M) as a between-subjects factor and time (week) as a within-subjects factor. We will use the group x time interaction to estimate and test treatment group differences at week 24 (primary endpoint). In fitting the mixed effects model with residual maximum likelihood, a variance-covariance structure will be selected based on criteria such as the Akaike's Information Criterion (AIC). The results from the mixed model will be summarized by mean (SE) for each treatment group at week 24. Secondary analyses comparing IBT+M and IBT+P in changes in hunger, satiety, reinforcing efficacy of food, and impulsivity from randomization to week 24 will be conducted using similar analytic strategies, as will exploratory analyses of change in cardiometabolic risk factors, quality of life, and depression. Similar mixed effects models also will be used to compare differences in percent weight loss from randomization to week 24 between early non-responders treated with BT+M and early responders who attend a randomization visit and are treated with BT alone. Logistic regression will be used to examine differences between BT+M and BT+P in percent of subjects who achieve a post-randomization loss of $\geq 5\%$ and $\geq 10\%$ of initial body weight at week 24. Subjects who do not provide a week 24 weight will be considered as not having achieved the categorical weight loss.

9.2.1 Missing Data.

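### The randomized comparisons of secondary and exploratory continuous outcomes prespecify no adjustment for the week 0 value, giving up precision that is almost free

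*Combined protocol and SAP*

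**What the plan says.** Section 9.2 (Phase 2) fits the primary outcome with treatment group, time and their interaction, and reads the week 24 difference from the interaction. It then says that the secondary comparisons of the two arms "in changes in hunger, satiety, reinforcing efficacy of food, and impulsivity from randomization to week 24 will be conducted using similar analytic strategies". Exploratory cardiometabolic, quality of life and depression outcomes are handled alike. The text does not say whether the week 0 value is a response, a covariate or a mean held common to both arms.

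The only route by which a pre-randomization value enters as a covariate is the general rule earlier in 9.2: "If baseline imbalances are observed, the relevant variables will be included as covariates in analyses relevant to those outcomes". No threshold for imbalance is given.

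Most of the values needed are already planned. Section 3.1 says that the baseline assessments "will be repeated at randomization (week 0) and at week 24". Sections 8.2.1, 8.2.2 and 8.4 bear this out for the test-meal appetite ratings, delay discounting and the questionnaires. Section 8.3 takes the cardiometabolic measures at screening, week 0 and week 24. The computer task for the relative reinforcing value of food is the exception: section 8.2.2 schedules it at week -5 only.

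**The concern.** A change score subtracts the whole week 0 value, whatever its correlation with the week 24 value. When that correlation is well below 1, as is plausible for visual analogue ratings or delay discounting, the subtraction adds noise. Regression on the week 0 value removes only the part that predicts the outcome, so in large samples its residual variance is lower at any correlation below 1.

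Section 9.1 expects about 20 subjects per arm with week 24 data, and section 3.1 concedes that the design limits power for secondary aims. Recruiting more subjects is ruled out there on grounds of treatment burden, so efficiency in the analysis is one of the few means left. A rule that adds covariates only after looking at the data makes each outcome's model depend on chance and seldom delivers the gain.

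**Working it through.** **1. The plan's own figure.** The only Phase 2 power figure is for the primary outcome. Section 9.1 expects losses of "6.5% in BT+M and 2.0% in BT+P, with expected standard deviations of 5.5" percent, with "a randomized sample size of 50 non-responders (25 per group), assuming a 20% attrition rate", and says that this "will give us 81.5% power to detect between-treatment group differences at week 24 of 4.5" percent. Standardized difference: 4.5/5.5 = 0.818. Subjects per arm after attrition: 25 x 0.8 = 20. Noncentral t power:
- 20 per arm, one-sided 0.05: 81.5%, the stated figure
- 20 per arm, two-sided 0.05: 71.3%
- 25 per arm, two-sided 0.05: 80.9%

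Section 9.1 does not give the sidedness ("All power analyses were conducted using G*Power 3.1 at an alpha of .05"), while section 9.2 says "Analyses will be two-tailed with an alpha of 0.05". That mismatch is a separate matter. What carries over here is 20 per arm and a two-sided 0.05 test. No power is given for secondary or exploratory outcomes.

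**2. What the model estimates.** With one follow-up, separate group means at each visit and complete data, the week 0 to week 24 group x time contrast is the difference in mean change. This holds even when week 0 is modelled as a response.

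**3. Variance per subject, in units of the outcome variance.** Assume equal variances and between-visit correlation r (an assumption; the documents give none).
- Change score: 1 + 1 - 2r = 2(1-r)
- Adjusted for week 0: 1 - r^2. The saving is 1 - (1-r^2)/[2(1-r)] = (1-r)/2
- Adjusted for week 0 and the earlier value, all correlations equal: 1 - 2r^2/(1+r)

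| r | change | week 0 | both | saving, week 0 | saving, both |
|---|---|---|---|---|---|
| 0.3 | 1.40 | 0.91 | 0.862 | 35% | 38% |
| 0.5 | 1.00 | 0.75 | 0.667 | 25% | 33% |
| 0.7 | 0.60 | 0.51 | 0.424 | 15% | 29% |

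Estimating k covariates with N = 40 multiplies the adjusted variance by 1 + k/(N-k-3), which is 1.028 for one and 1.057 for two. The savings become 33%, 23% and 13% (week 0) and 35%, 30% and 25% (both).

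**4. If correlation fades with time.** Take 0.7 between week -5 and week 0, 0.5 between weeks 0 and 24, and 0.4 between weeks -5 and 24. The variance explained by both values is (0.25 + 0.16 - 2 x 0.5 x 0.4 x 0.7)/(1 - 0.49) = 0.13/0.51 = 0.255. The residual is 0.745, against 0.75 with week 0 alone, so the earlier value adds almost nothing and the total saving is about 25%.

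**5. Power for an assumed difference of 0.7 SD,** 20 per arm, two-sided 0.05, covariate penalty included. The noncentrality is 0.7/sqrt(2v/20), with v the variance above (times the penalty where adjusted) and 38, 37 or 36 degrees of freedom.

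| r | change score | week 0 | both, equal correlations |
|---|---|---|---|
| 0.3 | 45% | 61% | 62% |
| 0.5 | 58% | 69% | 73% |
| 0.7 | 80% | 85% | 90% |

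At r = 0.5, for example, the change score gives 0.7/sqrt(0.100) = 2.21. Week 0 adjustment has v = 0.75 x 1.028 = 0.771 and gives 0.7/0.278 = 2.52.

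**6. The imbalance rule.** A simulation of 20,000 trials per r, 20 per arm, took imbalance as p < 0.05 on the week 0 value (an assumed threshold). The rule adjusted in about 5% of trials. It cut the variance by 9%, 6% and 3% at r = 0.3, 0.5 and 0.7, against 33%, 23% and 12% when week 0 was always included.

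**The case against.** The best reply is that the plan is silent on adjustment, not opposed to it. The promise of similar strategies is compatible with a common week 0 mean, which would already recover the week 0 gain, and the imbalance rule does allow covariates. A reader might infer that adjustment is excluded; the text does not say so. But it does not commit to adjustment either, and step 6 shows that the imbalance rule is a poor substitute, at least at the threshold tried.

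Several limits on scope also stand:
- Exact equality with a change-score test needs complete data, while section 9.1 expects 20% attrition and section 9.2.1 uses all available data by likelihood.
- The past-week appetite ratings are taken at treatment visits (3.3.2) and so have several follow-ups. Blood pressure is also taken at many visits (10.6), although its outcome schedule has one follow-up (8.3).
- The reinforcing-value task has no week 0 value.
- For weight in kg the between-visit correlation is plausibly very high. At r = 0.9 the week 0 saving is only 5%.
- Early responders were not randomized against BT+M; the groups are defined by run-in weight loss. A common week 0 mean has no justification there.

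Nor are these comparisons the trial's only evidence on how the drug works. The treatment-visit ratings bear on that too, and neuropeptides and gastric emptying are re-measured at week 24 (8.2.1), although no Phase 2 analysis of them is listed.

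Finally, section 9.1 calls the research preliminary. That tempers the urgency; it is no reason to decline a gain that needs no new data.

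**Conclusion.** The point holds as a free gain in precision for the randomized BT+M versus BT+P comparisons of continuous secondary and exploratory outcomes that have a week 0 value and one follow-up. Under assumed correlations of 0.3 to 0.7, week 0 adjustment saves about 35% to 15% of the variance, or 33% to 13% after the small-sample penalty.

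A reader might conclude that the plan wastes a third of its information. The documents do not support that as a fact: it needs a correlation near 0.5, both earlier values, and equal correlations across a gap of about 5 weeks and one of 24 weeks or more. With fading correlation the total is about 25%, nearly all of it from week 0. The 0.7 SD difference behind the power figures is likewise an assumption.

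A reader might also infer bias. There is none from this source: under randomization the change-score contrast is unbiased, and a chance week 0 difference shows up as variance. The stated power for the primary endpoint is unaffected.

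**What to change.** Add to section 9.2: each continuous secondary and exploratory outcome in the randomized comparison that has a week 0 value will be compared between arms at week 24 by ANCOVA, or by a mixed model, that always includes the week 0 value (as a covariate or as a mean constrained equal across arms), regardless of observed imbalance. The earlier value (week -5, or screening for cardiometabolic measures) may be added where collected; name the outcomes in advance. State that the common week 0 mean does not apply to the comparison of BT+M with early responders.

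The cost is a sentence or two and one or two degrees of freedom per model. No new data or visits are needed.

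### The 10% weight-loss endpoint is to be tested by logistic regression with no stated test statistic or sparse-cell method, although the plan's own assumptions give about a 22% chance of no placebo achiever

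*Combined protocol and SAP*

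**What the plan says.** Section 9.2 (Phase 2) gives the method for the categorical secondary endpoints: "Logistic regression will be used to examine differences between BT+M and BT+P in percent of subjects who achieve a post-randomization loss of" at least 5% and at least 10% of initial weight at week 24. Subjects without a week-24 weight "will be considered as not having achieved the categorical weight loss", so the denominator remains everyone randomized. The general rule in the same section is: "Analyses will be two-tailed with an alpha of 0.05".

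The section does not say which test is taken from the logistic model (Wald, score or likelihood ratio). It names no penalised or exact version and no fallback for a zero cell. Fisher's exact test appears in 9.2 only for comparing baseline characteristics between arms.

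Section 9.1 supplies the planning values: losses of "6.5% in BT+M and 2.0% in BT+P, with expected standard deviations of 5.5" percent, and "a randomized sample size of 50 non-responders (25 per group), assuming a 20% attrition rate". The Study Summary instead gives 60 randomized. Neither section gives an expected proportion or a power figure for the 10% endpoint.

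**The concern.** With 25 per arm and a placebo mean of 2.0%, a 10% loss on placebo is a rare event. If no placebo subject reaches it, the logistic likelihood keeps rising as the treatment coefficient grows. The odds ratio then has no finite estimate, its standard error becomes enormous, and the Wald p-value goes towards 1. This happens in exactly the tables where the data most favour phentermine.

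The proportion losing at least 10% is a listed secondary objective and endpoint. It could be reported as non-significant, or with an unusable odds ratio, when the counts point clearly to an effect. Any rescue method would then be chosen after seeing the empty cell, and the candidate methods differ widely in power and in type I error.

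**Working it through.** **1. The plan's own figure.** Section 9.1 says its sample "will give us 81.5% power to detect between-treatment group differences at week 24 of 4.5" points. With d = 4.5/5.5 = 0.818, a two-sample t-test gives 81.5% for 20 per arm one-sided, 80.9% for 25 per arm two-sided, and 71.3% for 20 per arm two-sided. The stated figure is therefore reproducible from these means and SD. Which variant was used does not affect the counts below.

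**2. Chance of losing at least 10%,** assuming normally distributed percent loss (not stated in the plan for this endpoint):
- Placebo: 1 − Φ((10 − 2.0)/5.5) = 0.0729
- Phentermine: 1 − Φ((10 − 6.5)/5.5) = 0.262

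**3. Missing counted as failure,** 20% attrition (multiply by 0.8): 0.0583 and 0.2098. Expected achievers among 25: 25 × 0.0583 = 1.46 and 25 × 0.2098 = 5.25.

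**4. Sparse placebo cell.**
- P(none) = (1 − 0.0583)^25 = 22.3%
- P(at most one) = 22.3% + 25 × 0.0583 × 0.9417^24 = 56.7%

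| Variation | P(no placebo achiever) |
|---|---|
| SD 4.5 | 46% |
| SD 5.0 | 33% |
| SD 6.0 | 15% |
| 20 completers per arm only | 22.0% |
| 25 per arm, no attrition | 15.1% |
| 30 per arm (60 randomized), 20% attrition | 16.5% |

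**5. What each test does with 0/25 v 5/25.** The unpenalised fit stops at a coefficient of about 22.2 with a standard error near 15,892, so Wald p = 0.999. For the same table, likelihood ratio p = 0.006, score p = 0.018, Firth p = 0.020 and Fisher p = 0.050 (0.0502, just short of significance). In the unadjusted two-group model, Firth's estimate equals adding one half to each cell, so its odds ratio is finite: (5.5 × 25.5)/(20.5 × 0.5) = 13.7.

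**6. Power and type I error at 25 per arm,** by enumerating all 26 × 26 outcomes at two-sided 0.05, with Wald counted as non-significant when a cell is empty:

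| Test | Power | Null rejection, both arms 5.8% |
|---|---|---|
| Wald | 12.7% | 0.03% |
| Fisher | 20.2% | 0.15% |
| Firth (penalised LR) | 36.5% | 2.6% |
| Score | 37.0% | 2.6% |
| Likelihood ratio | 39.7% | 8% |

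The 5.8% null rate flatters Firth and score and is harsh on Wald. At the pooled rate, (0.0583 + 0.2098)/2 = 13.4%, Wald rejects 1.5% of the time, and Firth and score about 5.3%. At 30 per arm the power gap persists: Wald 19.6%, Firth 37.9%.

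**7. The 5% endpoint.** The same steps give 0.8 × [1 − Φ(3/5.5)] = 0.234 on placebo and 0.8 × [1 − Φ(−1.5/5.5)] = 0.486 on phentermine. P(no placebo achiever) is 0.13%, and power is 46.7% (Wald) v 46.9% (Firth).

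**The case against.** The strongest reply is that the plan never names the Wald test. A reader might infer that 9.2 commits to a test that cannot work, and the text does not support that. The score test from the same unpenalised model matches Firth for the unadjusted comparison, in both power and type I error. The likelihood-ratio test also detects 0 v 5, though it is liberal in tables this sparse. This stands: for testing, the gap is an unspecified statistic, and ordinary logistic regression does not fail as such. Two things remain. The odds ratio is not finite with an empty cell, whichever test is chosen. And Wald is the coefficient test usually read from logistic output, so leaving the choice open leaves power anywhere from about 13% to 40%.

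A reader might also extend the point to the 5% endpoint, since one sentence covers both thresholds. The figures do not support that.

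The endpoint is secondary, section 9.1 calls the research preliminary, and the comment in 3.1 concedes that the sample could not be enlarged to power secondary aims. Even with Firth, power is 36.5%, so a non-significant result is the likelier outcome under every test considered. A divergent odds ratio would also be obvious, and the raw counts could still be reported. All of this limits the consequence. It does not justify leaving the method to be settled once the counts are known.

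**Conclusion.** The point holds for the 10% endpoint only. Under the plan's planning values, about one trial in five (22%) would have no placebo achiever. It would then have no finite maximum-likelihood odds ratio, and the customary coefficient test could not reject. Across all outcomes, that test has roughly a third of the power of Firth or score (12.7% v 36.5% and 37.0%).

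These figures rest on normally distributed percent loss, SD 5.5%, 25 per arm and 20% attrition in each arm. The 22% moves to 15% at SD 6.0, to 46% at SD 4.5, and to 16.5% with the Study Summary's 60 randomized. It should not be read as a fault in the primary mixed-model analysis, which is unaffected.

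**What to change.** In 9.2, pre-specify for the 10% endpoint Firth penalised-likelihood logistic regression with a penalised likelihood-ratio test and a profile-likelihood confidence interval. This gives a finite odds ratio with an empty cell. It also accommodates the covariates that 9.2 would add after a baseline imbalance. For the unadjusted comparison the score test is an equally good test, but it does not by itself supply a finite odds ratio. Report the risk difference with a score-based or exact confidence interval beside it.

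The 5% endpoint does not need the change, though the same method may be used for both for consistency. The cost is a sentence or two in 9.2, written before unblinding, with no new data and no added subjects.
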